Name:	
Internal code:	
Pharmaceutical form:	
[Strength/Concentration]:	
Dosage (total daily dose):	
Route:	
Duration of administration:	
Dose regimen:	
Location of treated area:	
Efficacy endpoints:	Percentage of subjects with an IGA Score of 0 (clear) or 1 (almost clear). Change from Baseline in Pruritus. Change from Baseline in %BSA.
Safety assessment:	Safety assessments include AE evaluation, vital signs/physical examination, and laboratory evaluations including hematology, chemistry, 1, 25(OH)2D, 25(OH)D, PD serum and urinary assessments (see Pharmacodynamic assessment below), eCRF AE forms will be reviewed periodically to monitor the ongoing safety of the study.  An Independent Data Monitoring Committee (IDMC) will be established for this study to monitor general subject safety and specifically parameters relating to calcium metabolism, and biochemistry.
Safety endpoints:	Safety endpoints include: Serum albumin-adjusted calcium, urine calcium:creatinine ratio, phosphorus, and PTH.
Pharmacokinetic assessment:	PK assessment: to evaluate the plasma concentration of calcitriol. One single blood sample at screening and baseline to assess the endogenous levels and its variability, then a single pre-dose blood sample (C t ) will be collected at Week 4, Week 12, Week 26, and Week 30 in approximately 9 subjects 2 to 6 years and 11 months of age.
Pharmacodynamic assessment:	PD Serum (non-fasting): calcium, phosphorus, albumin (in order to calculate the serum albumin-adjusted calcium) and PTH.  PD Urine: Urine calcium and creatinine on 24-hour urine collection, whenever possible, or a urine sample after fasting for 4 hours in order to calculate Urine calcium : creatinine ratio.

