## GALDERMA R&D

Protocol No.: RD.06.SPR.18131 V03 - 02 Dec 2015 eUS

Page 14 of 83

 Visit window of  $\pm$  3 days.

 Physical Examination to include: weight and review of systems: skin, cardiovascular, respiratory, abdomen, head and neck, musculoskeletal, neurological, lymph nodes and psychological. Height is to be evaluated at Screening visit only. Vital Signs to include: blood pressure, pulse rate

 Reconfirm that subject continues to meet inclusion/exclusion criteria.

 Total amount of Study Drug applied to involved skin should not to exceed 0.5 g/kg of body weight or 28g per day (whichever is the lower). First application to be made under the supervision of the investigator or designee. Record daily administration on dosing calendar. Dosing calendar to be checked at each visit after Baseline.

 Or at any time in case of early termination.

 The Cetaphil® Moisturizing Cream and Cetaphil® Gentle Skin Cleanser or equivalents will be provided by the Sponsor

 Events occurring after the Informed Consent Form and Assent Form (when applicable) have been signed should be recorded as Adverse Events in the eCRF

 Any therapy or medication other than study ointment will be noted on the Drugs/Therapies Form. Subjects that require a wash-out period of a prohibited therapy for >2 weeks, should be screen failed and may re-screen 1 time after completion of the washout period.

 PD Serum (non-fasting): calcium, phosphorus, albumin (in order to calculate the serum albumin-adjusted calcium) and PTH.

 PD Urine: Urine calcium and creatinine on 24-hour urine collection, whenever possible, or a urine sample after fasting for 4 hours in order to calculate Urine calcium : creatinine ratio. Subjects that are toilet-trained should be actively encouraged to complete 24-hour urine collection. A urine collection container/material will be given to the subject / subject's parent/legal guardian with the instruction to start collecting urine as of this visit and to bring the container back after the 24-hour/4-hour collection.

 Laboratory testing (full panel) will be completed at Week 30 for subjects in the PK group. For all other subjects, laboratory testing at Week 30 will be completed at Investigator's discretion.

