 Subjects with suspected kidney stones should temporarily discontinue study drug and will be referred to their Primary Care Physician (PCP) for care in tandem with Sponsor consultation of the IDMC.

 The visit before: Distribute container and provide instructions for 24-hour urine collection to be started 1 day prior to Week 12 and Week 26/ET visits. The study site should contact the parent/legal guardian 48 hours prior to the visit to remind them to start the urine collection.

 Subjects may re-screen one time with written approval from the Sponsor prior to re-entry into the study.

 At Baseline, the study nurse show the subject's parents how to apply the drug.

 Visit window of  $\pm$  5 days.

 For subjects in the PK group, a single blood sample at Screening and Baseline will be taken, then a single pre-dose blood sample will be taken at Weeks 4, 12, 26 and 30, to assess the calcitriol plasma concentration. The volume of each blood sample will be 5 mL. A total volume of 30 mL will be collected during the study for PK assessment.

 Serum PD will be assessed during Baseline visit only for subjects 2 to 6 years and 11 months of age in whom PK analysis will be conducted in order to assess PK/PD relationships at Baseline for these subjects.

Unscheduled visit: When necessary and exceptionally, because of either an AE needing a specific treatment, AE leading to withdrawal from the study, laboratory result(s) that warrant further testing, or other reason.

An ongoing dialogue between subject, parent/legal guardian and investigators focusing on all aspects of the trial is encouraged. Any new information that arises in relation to the trial and that might affect the willingness of the subject and/or parent/legal guardian should be discussed. This brief discussion should be documented during each study visit.

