**5.4 Exclusion criteria**

1. Subjects with guttate psoriasis, pustular psoriasis, erythrodermic psoriasis or active infection (i.e., an infection associated with fever, swollen lymph nodes, and/or signs of localized inflammation of tissue and/or joints). *Note: allergic or vasomotor rhinitis is not exclusionary.*
2. Any newly diagnosed genetic or congenital condition, uncontrolled or serious disease, or any medical or surgical condition, that may either interfere with the interpretation of the clinical trial results, and/or put the subject at significant risk (according to Investigator's judgment) if he/she participates in the clinical trial.
3. Known or suspected allergies or sensitivities to any components of any of the study drugs (see Investigator's Brochure/Product label).
4. Female who is lactating.
5. Female who intends to conceive a child during the clinical trial.
6. Current participation in any other clinical trial of a drug or device OR participated in a clinical trial of a drug or device within 1 month prior to baseline.

7. The subject has received, applied or taken the following treatments within the specified time frame prior to the Baseline visit:

Topical treatment(s) or Procedures:	
• Corticosteroids or topical immunomodulators	2 weeks
• Tar (on areas to be treated with study drug)	2 weeks
• Vitamin D derivatives	2 weeks
• Vitamin A derivatives	2 weeks
• Intralesional steroid injections	4 weeks
Systemic treatment(s):	
• Homeopathic or herbal preparations	1 weeks
• Calcium containing products	2 weeks
• Immunomodulators and biologics known to affect psoriasis	4 weeks
• Corticosteroids or ACTH analogs	4 weeks
• Phototherapy/PUVA therapy	4 weeks
• Laser therapy	4 weeks

8. The subject or subject's parent /legal guardian is unwilling to refrain from use of prohibited medication during the clinical trial (see Section 5.5.5).
9. The subject is vulnerable (such as deprived from freedom) as defined in Section 1.61 of International Conference on Harmonisation (ICH) Guideline for Good Clinical Practice (GCP).
10. The subject has hypercalcemia (serum albumin-adjusted calcium above the upper normal range) at Screening.
11. The subject has urinary calcium:creatinine ratio above the upper normal range at Screening.
12. The subject has history or signs and symptoms of urolithiasis.
13. Subjects with known or suspected disorders of calcium metabolism.

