14. Subjects with liver dysfunction, defined as laboratory AST or ALT >2x ULN or Total bilirubin >1.5x ULN.
15. Subjects with creatinine clearance <85mL/min per 1.73 m^2 at Screening. (Shull, et al, 1978)

Note:

Creatinine clearance is to be calculated using the Schwartz Equation:

$$\text{Creatinine Clearance} = k \times H / \text{Scr.}$$

For children 1-12 and adolescent girls 13-16 years and 11 months old, k=0.55. For adolescent boys 13-16 years and 11 months old, k=0.7. H=height at screening (cm). Scr=serum creatinine (mg/dL) at screening. (Schwartz 1976).

16. Subjects with concomitant medical or dermatological disorder(s), which might preclude accurate evaluation of the psoriasis.
17. Subjects with underlying systemic or other dermatological conditions that require the use of systemic supplements of calcium or vitamin D. (Subjects taking oral calcium and vitamin D for prophylactic purposes must be on a stable dose for at least 4 weeks prior to screening and are not to exceed the Recommended Daily Allowance for calcium (1,300 mg for subjects aged 12-16 years and 11 months and 1,000 mg for subjects less than 12 years) or Vitamin D (600 IU).
18. The Subject has Vitamin D deficiency ( $25(\text{OH})\text{D} < 20 \text{ ng/mL}$ ) at Screening (Note: Subjects with  $25(\text{OH})\text{D} < 20 \text{ ng/mL}$  at screening, may undergo re-screening after at least 4 weeks of Vitamin D deficiency treatment to determine eligibility.).
19. The subject is planning excessive exposure to the sun or ultraviolet light during the study (i.e. natural or artificial sunlight, including tanning booths and sun lamp).
20. Subjects with clinically significant blood loss within the last 3 months prior to screening, per Investigator discretion.
21. The Subject has clinically significant abnormal values of the safety laboratory parameters at Screening (See Section 7.2.2).
22. The Subject has secondary hyperparathyroidism or PTH above Upper Limit of Normal at Screening.

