### 7.4 Pharmacokinetic assessment

#### 7.4.1 Blood sampling

The systemic level of calcitriol will be assessed at each visit using a single blood sample ( $C_t$ ) according to the Schedule of Assessments (Table 2). To avoid tube contamination, drug product application and blood draws have to be performed in different rooms. Blood samples will have to be collected in either the morning or evening (to be determined at screening according to the subject's lifestyle). In addition, for the blood samples to be drawn during the treatment period (i.e. at Week 4, Week 12 and Week 26), the sampling has to occur 12 hours ( $\pm 1$  h) after the last product application. Blood sampling procedure and handling of samples will be described in a separate document.

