### **7.4.3 Pharmacokinetic measurements**

The pharmacokinetic analysis will be carried out by GALDERMA R&D, Sophia Antipolis, France. The  $C_t$  mean values and the standard deviation (SD), will be calculated and reported.

Assessments occurring at screening and baseline (before product application) will allow determining calcitriol endogenous levels variability. Pre-dose samples performed at Weeks 4, 12, and 26 will document the calcitriol plasma concentration during the treatment period. Blood sample drawn at week 30 visit allow determining the calcitriol plasma concentration one month after the last drug product application.

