### 9.1.6 Pharmacokinetics analysis

$C_t$  will be submitted after logarithmic transformation (Ln), to paired comparisons of Baseline and each subsequent time point. Ninety percent confidence intervals of the pairwise differences will be calculated using the Student's t statistic. The limits of the intervals will be back-transformed into exponential to obtain 90% confidence intervals of the ratios of geometric means between time points, on the original scale.

PK/PD relationships will be investigated by correlating  $C_t$  with appropriate PD parameters, using Spearman coefficient and graphical illustrations.

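### Should the calcitriol ratios use the mean of the Screening and Baseline samples as their reference, instead of Baseline alone?

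*Protocol*

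**What the plan says.** Protocol 9.1.6, repeated in the Synopsis, log-transforms Ct and submits it "to paired comparisons of Baseline and each subsequent time point". It uses Student's t and back-transforms the 90% limits to ratios of geometric means. The later time points are Weeks 4, 12, 26 and 30.

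Two pre-drug samples exist. Table 2, footnote 17 states that for the PK group "a single blood sample at Screening and Baseline will be taken". Section 7.4.3 gives the purpose: "Assessments occurring at screening and baseline (before product application) will allow determining calcitriol endogenous levels variability". The Synopsis agrees: "One single blood sample at screening and baseline to assess the endogenous levels and its variability".

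Three provisions bear on whether the two samples are alike:

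- **Time of day.** Section 7.4.1 has blood drawn "in either the morning or evening (to be determined at screening according to the subject's lifestyle"), so the slot is fixed only at the visit where the first sample is taken.
- **Washout.** Exclusion 7 in section 5.4 counts back from Baseline: "The subject has received, applied or taken the following treatments within the specified time frame prior to the Baseline visit". Its list includes topical vitamin D derivatives and systemic calcium products, each with 2 weeks. Table 2, footnote 8 adds that "Subjects that require a wash-out period of a prohibited therapy for >2 weeks, should be screen failed"; shorter washouts may run between the two visits.
- **Re-screening.** Under Exclusion 18, children with vitamin D deficiency "may undergo re-screening after at least 4 weeks of Vitamin D deficiency treatment".

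Section 9.2.1 states that no formal sample size calculation was made. The SAP has no pharmacokinetic section.

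**The concern.** Calcitriol is endogenous, so the ratios are only as good as the pre-drug reference. With one reference value per child, that value's assay error and day-to-day variation enter all four ratios. A second pre-drug sample has already been drawn at 5 mL from children aged 2 to 6 years and 11 months, and 9.1.6 leaves it out of the reference. Averaging two equally noisy, independent values halves the reference variance at no extra blood. With about 9 children behind a stated secondary objective, a narrower interval for free is attractive. If the gain were dependable, leaving it out would be a small but avoidable loss of information.

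**Working it through.** **Inputs.** From the documents: n of about 9; 90% interval with Student's t, so t(0.95, 8 df) = 1.860; nominal gap between the draws 14 days (Screening at Day -14), or 9-19 days with the ±5-day Baseline window. The documents state no interval width, within-child variance or serial correlation, so there is no plan figure to reproduce. What follows is a range under assumptions.

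**Model.** Set the within-child variance of ln(Ct) to 1, of which a share g is independent noise and the rest is serially correlated, with correlation ρ per 2 weeks. Then r(x) = (1-g)·ρ^(x/2), with x in weeks. For a visit at week w, gap d weeks and between-child variance of the change τ²:

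- Baseline only: V1 = 2 - 2r(w) + τ²
- Mean of both: V2 = 1 + [2 + 2r(d)]/4 - [r(w+d) + r(w)] + τ²
- Relative width = √(V2/V1). With the same n and degrees of freedom, t cancels.

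**Best case** (ρ = 0, τ² = 0): √(1.5/2) = 0.866, so 13.4% narrower at every visit.

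**Serial correlation only** (g = 0, τ² = 0, d = 2). Worked example, ρ = 0.9, Week 4: V1 = 2 - 2(0.81) = 0.38; V2 = 1 + (2 + 1.8)/4 - (0.729 + 0.81) = 0.411; √(0.411/0.38) = 1.040. Change in width:

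| ρ per 2 weeks | Week 4 | Week 12 | Week 26 |
|---|---|---|---|
| 0.5 | -4.3% | -6.4% | -6.5% |
| 0.7 | -0.1% | -3.3% | -3.8% |
| 0.8 | +1.9% | -1.6% | -2.4% |
| 0.9 | +4.0% | +0.2% | -0.8% |
| 0.95 | +5.0% | +1.1% | 0.0% |

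As ρ approaches 1 the relative width tends to √(1 + d/(4w)). At Week 4 that is √(1 + 2/16) = 1.061; with a 19-day gap it is √(1 + 19/112) = 1.082. At Week 12 with d = 2 it is √(1 + 2/48) = 1.021. So the loss is not confined to Week 4.

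**Unequal variance.** With independent errors and Screening variance k times that of Baseline, V2 = 1 + (1 + k)/4. At k = 2 the gain is 1 - √(1.75/2) = 6.5%; at k = 3 it is nil.

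**Moderate penalties together** (ρ = 0.5, g = 0, τ² = 1, 3 of 9 children on Baseline alone), Week 26: V1 = 3.000, V2 = 2.750, mixture (3·3.000 + 6·2.750)/9 = 2.833; √(2.833/3.000) = 0.972, so 2.8% narrower (1.7% at Week 4). With the same penalties and ρ = 0.8, Week 4 is 0.5% wider and Week 26 is 1.0% narrower. At an assumed CV of 30%, s = √ln(1.09) = 0.2936. The Week 26 half-width goes from 1.860 × 0.2936 × √(3.000/9) = 0.315 to 0.306, a gain of 0.009. Around a ratio of 1, 0.73-1.37 becomes 0.74-1.36.

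**What the gain is bought with.** The averaged reference carries half of any systematic Screening-to-Baseline difference.

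- A common shift of 0.10 in Screening ln(Ct) moves the reference by 0.05 and every ratio by the factor exp(-0.05) = 0.951.
- Eligibility is judged on Screening laboratory values. Suppose the top 15% on a value correlated c = 0.2-0.4 with the transient part of Screening ln(Ct) are excluded. The reference then moves by ½·c·φ(z)/0.85·s = 0.008-0.016, with z the 85th normal percentile. If all of the expected 40% screen failures came from one such value, it moves by 0.019-0.038.
- A direct check of Screening against Baseline has a 90% half-width of 1.860 × 0.2936 × √(2/9) = 0.257 with uncorrelated errors, or × √(1/9) = 0.182 at ρ = 0.5. A shift of 0.10 would go unseen.

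The 0.009 gain is therefore no larger than the smaller selection shift and well below the 0.05 reference shift.

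**The case for a change.** The strongest case for averaging is that real assay and day-to-day noise is seldom negligible. If 25% of the within-child variance is independent, averaging is at least 4.4% narrower at every visit for any serial correlation; at 50% it is at least 7.6% narrower. From about 8% independent noise, Week 4 no longer widens at a 14-day gap. Children without a comparable Screening sample could fall back to Baseline alone, so none need be lost, and section 9.1 would let the change go into an amended SAP before database lock.

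Most of this stands: in most plausible settings averaging narrows the interval somewhat. But these percentages assume equal variance and no systematic difference between the two draws, and the provisions on time slot, washout and re-screening leave that open. Guarding against it takes several fallback conditions, a drift check with little power, and two sets of four intervals from about 9 children. A statistician could choose that as a prespecified sensitivity analysis. That section 9.1.6 makes the simpler choice is not a defect.

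**Conclusion.** The concern does not hold. The planned paired comparison gives valid intervals against the last pre-drug sample, the one for which washout is complete by protocol. It also fits SAP 7.5, which takes efficacy Baseline as the last data before first application and, among several pre-drug laboratory values, the one closest to it. The Screening sample is not wasted, since the protocol assigns it to describing endogenous variability.

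The alternative runs from 13.4% narrower to about 6% wider at Week 4 (8% at a 19-day gap), with about 2-3% narrower in the moderate combined case without independent noise. Against that stands a possible bias of similar or larger size that about 9 children cannot reveal. These figures rest on assumed correlation, noise share and CV, because the documents give none. The finding that the plan is valid does not rest on them. The choice of reference is a matter of preference.

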A PK/PD study (SPR.18102) was conducted from August 2006 to September 2009 on 25 adolescents (12-17 years old; mean age: 14.7 years) with plaque psoriasis affecting 10 to 35% BSA (mean: 17.8%). Serum calcitriol levels were investigated at baseline and after 21 days of treatment with Vectical® (calcitriol 3µg/g ointment). Subjects received two applications per day and up to 15 g of formulation per application, depending on the total BSA and on the percentage of psoriasis-involved BSA. There was no significant variation of calcitriol levels during treatment. The overall mean ( $\pm$ SD) value of maximum calcitriol plasma levels (Cmax) was 76 $\pm$ 24 pg/mL at Baseline (endogenous levels) and 73 $\pm$ 22 pg/mL after 3 weeks of treatment. Regarding age stratification, the mean Cmax and AUC0-9hr or AUC0-12hr at Baseline were higher in the 12 to <15 years than in the 15 to 17 years (respectively 26% higher for Cmax and 19% higher for AUC0-9hr and AUC0-12hr). The same tendency was observed after 21 days of application. The plasma calcitriol levels (Cmax) appeared to be 21% higher in the 12 to <15 years age group compared to the 15 to 17 years age group and AUC0-9hr and AUC0-12hr, were approximately 17% higher. However, in each stratum, the calcitriol levels after 21 days of treatment were similar to the baseline levels. Overall, the repeated application of calcitriol 3 µg/g ointment did not result in an increased systemic exposure.

Furthermore, no correlation could be established between percentage of psoriasis-involved BSA and  $AUC_{0-9h}$  in this study. Therefore, in study 18131, repeated applications of Vectical® are not expected to increase endogenous levels of calcitriol.

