### **Pharmacokinetic (PK) Assessment:**

- Plasma concentration of calcitriol (1, 25(OH)2D) will be assessed using a single pre-dose blood sample ( $C_t$ ) in a subset of approximately 9 subjects aged between 2 to 6 years and 11 months old.

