## 2.2 Clinical hypothesis

Long term use (26 weeks) of calcitriol 3 mcg/g ointment is safe and efficacious in pediatric subjects (2 to 16 years and 11 months of age, Version R03) with mild to moderate plaque psoriasis.

The calcitriol absorption in pediatric subjects (2 to 6 years and 11 months of age) is expected to be comparable to that in adults and adolescents, with no significant impact on calcium/phosphorus metabolism.

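### Section 9.1.6 compares each visit's Ct with a single Baseline sample in about 9 children; one pooled within-child contrast on samples already scheduled would be about 35% narrower, and the intervals need a stated reading rule

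*Protocol*

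**What the plan says.** Calcitriol plasma level is the secondary objective (protocol synopsis and section 2.1), assessed "in a subset of approximately 9 subjects aged between 2 to 6 years and 11 months old". The schedule of assessments takes one PK sample at Screening, one at Baseline, then pre-dose samples at Weeks 4, 12, 26 and 30. Section 7.4.3 uses Screening and Baseline to describe variability of endogenous levels, and Weeks 4, 12 and 26 to describe levels on treatment. On the last sample it says: "Blood sample drawn at week 30 visit allow determining the calcitriol plasma concentration one month after the last drug product application".

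Section 9.1.6, repeated in the synopsis, submits ln Ct "to paired comparisons of Baseline and each subsequent time point". For the interval method it says "Ninety percent confidence intervals of the pairwise differences will be calculated using the Student's t statistic", and the limits are back-transformed "to obtain 90% confidence intervals of the ratios of geometric means between time points, on the original scale". Neither the comparison nor any other part of section 9 uses the Screening sample, pools the on-treatment visits, or states how an interval is to be interpreted. The SAP has no PK objective, variable, method or table. Section 9.2.1 reports no formal sample size calculation, and nothing is said about the precision expected from 9 children.

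**The concern.** The protocol expects a null result. Section 1 says that repeated applications "are not expected to increase endogenous levels of calcitriol". In a subset this small, an interval that covers 1 is a common outcome even when levels have risen. Without a reading rule, such an interval could be taken as support for no increase in the youngest children.

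The chosen comparison also makes the intervals wider than they need to be. Each one sets a single noisy on-treatment value against a single noisy Baseline value, so the information in the other scheduled samples from the same child does not reach the estimate. At stake is how much the only analysis in the trial with confidence intervals can say about systemic exposure in children aged 2 to 6 years and 11 months.

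**Working it through.** **Plan's own figure.** The only sample-size figure is 100/(1 − 0.40) = 166.7, so 167 screened. It reproduces, but says nothing about the PK subset.

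**Inputs**
- n = 9, so 8 degrees of freedom (protocol 2.1, PK assessment).
- Two-sided 90% t interval (9.1.6). It lies wholly above 1 when the paired t statistic exceeds t(0.95; 8) = 1.860, so each interval carries a 5% chance of a false rise.
- Within-child CV is not in the documents, so I take 15% to 30%. The nearest figure is the SPR.18102 baseline Cmax in adolescents, 76 ± 24 pg/mL, a between-child CV of 24/76 = 0.316 and an ln-scale variance of ln(1 + 0.316²) = 0.095. If that total applied here, a within-child CV of 20% would mean a within-child correlation of 1 − 0.0392/0.095 = 0.59, and 30% a correlation of 1 − 0.0862/0.095 = 0.09. On that basis 30% is near the unfavourable end.
- A true ratio of 1.25 is illustrative: ln 1.25 = 0.2231.

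**Formulas.** σ = √ln(1 + CV²).
- Single visit minus Baseline: SD = σ√2.
- Mean of three on-drug minus mean of two pre-drug samples: SD = σ√(1/3 + 1/2) = 0.913σ.
- Noncentrality = 0.2231 × √9 / SD. Miss = P(noncentral t, 8 df ≤ 1.860).

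**Worked cases**
- CV 20%: σ = 0.198. Single: SD 0.280, noncentrality 2.39, miss 30%. Pooled: SD 0.181, noncentrality 3.70, miss 4%.
- CV 30%: σ = 0.294. Single: SD 0.415, noncentrality 1.61, miss 57%. Pooled: SD 0.268, noncentrality 2.50, miss 26%.

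| Within-child CV | Miss, one visit vs Baseline | Miss, pooled contrast |
|---|---|---|
| 15% | 11% | 0.3% |
| 20% | 30% | 4% |
| 25% | 46% | 14% |
| 30% | 57% | 26% |

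**Width.** √(5/6)/√2 = 0.645, so the ln-scale interval is about 35% narrower at any CV.

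**Any of three visits.** In simulation (shared Baseline, independent errors, constant effect), counting a rise at any of Weeks 4, 12 or 26 lowers the miss for a 25% rise to 9% (CV 20%) and 30% (CV 30%). It gives a false rise in 12% of trials, against 5% for the single pooled interval.

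**Excluding a rise.** If Ct is truly unchanged, the chance that the upper limit falls below an illustrative 1.25 is 70% (CV 20%) or 43% (CV 30%) for one visit, and 96% or 74% for the pooled contrast. Covering 1 and excluding a given rise are different findings.

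**Fewer children.** With n = 7 (critical value 1.943, √7 in the noncentrality) the single-visit miss is 41% and 65%, and the pooled miss 11% and 38%.

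**Drift.** The on-drug samples centre on week (4 + 12 + 26)/3 = 14. Screening (nominal Day −14) and Baseline centre on week −1, so a steady drift in endogenous calcitriol would enter the contrast. Averaging the pre-drug mean with Week 30 at equal weight centres the reference on (−1 + 30)/2 = 14.5, which nearly cancels a linear drift.

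**The case against.** A reader might infer that the trial will declare no increase, or even no absorption, whenever each interval covers 1. The documents do not support that. No such rule is written, the synopsis says no inferential statistics are planned, and a geometric mean ratio with 90% limits is estimation, in which a wide upper limit would be visible.

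The nearest precedent is the account of SPR.18102, "There was no significant variation of calcitriol levels during treatment", followed by a conclusion of no increased systemic exposure. That account also gives Cmax of 76 ± 24 at Baseline and 73 ± 22 pg/mL on treatment, and says levels in each age stratum were similar to baseline, so it does not rest on non-significance alone. Section 2.2 expects absorption comparable to adults and adolescents, not none. Its phrase "with no significant impact on calcium/phosphorus metabolism" concerns a pharmacodynamic outcome and should not be tied to a Ct ratio.

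A reader might also take the single-visit miss rate as the chance that the trial as a whole overlooks a rise. Three on-drug visits are examined, and the any-of-three miss is much lower.

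The pooled contrast has limits of its own. Children who reach IGA 0 stop the drug but keep attending (section 3), so some on-treatment samples may be off drug. Section 9.1.4.1 leaves missing data as observed, which does not settle how to treat a child with an incomplete set. Averaging can hide a late rise.

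These objections stand as limits on the claim. They do not explain why the estimate should use only one of the two pre-drug samples, or why the reading of the limits is left open.

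**Conclusion.** The point holds as a matter of precision and interpretation for a secondary objective. A single-visit interval in 9 children misses a true 25% rise 30% to 57% of the time at within-child CVs of 20% to 30%, so one that covers 1 cannot by itself support no increase over endogenous levels. The pooled contrast cuts this to 4% to 26% with a 5% false-rise rate. Against the any-of-three reading the gain in misses is smaller (9% to 4%, and 30% to 26%), but false rises fall from 12% to 5%.

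The figures rest on an assumed within-child CV, an illustrative ratio of 1.25, independent within-child errors, complete data and a constant effect. Serial correlation would reduce the gain. Using Screening and Baseline as the reference avoids assuming that no drug effect remains at Week 30.

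**What to change.** In section 9.1.6, the synopsis and the SAP:

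1. Add one within-child contrast, mean ln Ct at Weeks 4, 12 and 26 minus mean ln Ct at Screening and Baseline, with a paired-t 90% interval back-transformed to a ratio.
2. Keep the visit-by-visit ratios, including Week 30, alongside it, so that a late rise or a persisting effect can be seen.
3. Add a sensitivity version that includes Week 30 in the off-drug mean, with its weight stated, to check for drift.
4. State that an interval covering 1 will not by itself be read as no increase, and that the upper 90% limit will be reported against a limit the sponsor fixes before database lock.
5. State in advance how a child missing one or more samples enters the contrast, and how samples taken while drug is stopped for IGA 0 are handled, since these dilute it.

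Leave the calcium/phosphorus wording in section 2.2 as it is.

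The cost is wording and one extra paired analysis; no blood draws or children are added. The sponsor has to commit to a limit, and must accept that the result may be inconclusive.
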